## **3 INVESTIGATIONAL PLAN**

### **3.1 General Schema of Study Design**

#### **3.1.1 Randomized Control Trial**

We propose to test the effects of digital versus standard literacy promotion using a randomized controlled trial design. One-hundred eligible parent-child dyads, with infants between 5 and 7 months of age, who present to one of the three CHOP Care Network practices (Cobbs Creek, Roxborough and Indian Valley) will be recruited and consented to participate in this 18-month long study. Participants will be stratified by clinic site and randomized to receive literacy promotion using 1) standard early reader board books or 2) digital electronic early reader e-books. Randomization sequences will be developed by the study team using computer-generated random numbers prior to study enrollment and will be placed in sealed opaque envelopes.

Randomization will ensure equivalence between groups on measured and unmeasured characteristics and is considered to be the strongest protection against bias in study design.

Participants randomized to the digital arm will receive the e-book version of [name] *Hop on Pop* for the 6 month well visit, Sandra Boynton's *Barnyard Dance* for the 9 month well visit, and Margaret Wise' *Goodnight Moon* for the 12 month well visit. Additionally they will receive information on the importance of early parent-child reading activity by pediatric clinicians using the Reach Out and Read framework. The appropriate e-books will be electronically gifted to the participants. Parents must have an appropriate mobile digital device such as a smart phone or tablet to download and open the digital e-books.

Participants randomized to the standard arm will receive the board book versions of [name] *Hop on Pop* for the 6 month well visit, Sandra Boynton's *Barnyard Dance* for the 9 month well visit, and Margaret Wise' *Goodnight Moon* for the 12 month well visit. Furthermore, participants will be provided information on the importance of parent-child reading activity by pediatric clinicians using the Reach Out and Read framework.

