Participants in both study arms will be followed every 3 to 4 months until the infants are between the ages of 12 and 18 months, 30 days. Information on reading activities and developmental outcomes will be collected in concert with scheduled well child visits. Differences in reading activities and developmental outcomes will be assessed between groups using intention-to-treat analysis. Parents will complete measures of demographics, health literacy, and maternal depressive symptoms at baseline. Parents will also complete measures of reading activity with their infant about 1 month after the child has, or is age-eligible for, their 6, 9, and 12 month well visits. The infant will also receive a developmental assessment at the second study visit which will happen about 1 month after they have, or are age-eligible for, their 12 month well visit. At this time the infant should be between 12 and 18 months, 30 days old. Secondary data to address these study questions does not exist, which will necessitate the collection of new data as proposed here. We anticipate that this collection of rich new data will support a careful assessment of the effects of digital vs. standard literacy promotion. The HER will be reviewed for children in both arms to count the number of well child visits and examine their vaccination history.

We anticipate collecting this data in conjunction with well child visits. In our experience, low-income families can be difficult to reach for study visits, even with appropriate study incentives. By coordinating data collection with the 6, 9, and 12 month well child visits timeframes, we can increase the probability of families attending both the well visits (to receive the Reach Out and Read Program materials) and the study visits (to collect measures of reading activity and development). In a previous study of 2100 children enrolled in a study of developmental screening, we were able to achieve a >90% follow-up rate by coordinating data collection with well child visits. In addition, our research staff can check the clinic schedule to ensure families have made timely well child visit appointments and then make reminder calls to families prior to these visits to encourage parents to attend. Study visits will be held at a location that is preferred

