Children in both study arms will be followed every 3 to 4 months until they are between 12 and 18 months, 30 days. Parents will complete study measures consisting of demographic characteristics, postpartum depression symptoms, health literacy, and adverse childhood experiences at the initial study visit. Parents will complete measures of reading activity at baseline, and via the REDCap survey sent by email, or completed in person, about 1 month after the infant has, or is age-eligible for, their 6, 9 and 12 month well visits. Differences in reading activities and language outcomes will be assessed between groups using intention-to-treat analysis.

Parents of children who are participating in the study will be informed of the results of their BSID-III testing in writing and/or by phone. Those whose child scores less than 1.5 standard deviations below the mean will be informed that their child's development is within the average range. Parents whose child scores 1.5 standard deviations or greater below the mean will be informed that their child is exhibiting delays in an area of their development. In addition, we will recommend that the parent inform their child's clinician of the results.

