#### **5.1.4 Reading Activity (StimQ)**

The StimQ is an office measure of cognitive stimulation at home available in Spanish and English, and the Read subscale of the StimQ contains questions on the frequency of parent-child reading activity and the number and variety of books at home. Psychometric analysis of the StimQ shows high internal consistency (Cronbach's Alpha=0.89) and test-retest reliability ( $r=0.84$ ) and moderate correlation with the Bayley Scales of Infant Development ( $r=0.52$ ,  $p<0.001$ ).

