### 6.3 Statistical Methods

Summary statistics will be obtained, and differences between digital and standard arms will be assessed using intention-to-treat analysis. Cross-sectional differences in StimQ scores between digital and standard groups at the 6, 9 and 12 month well visits will be assessed using t-tests. To determine how the effects of digital versus standard literacy is associated with language development, we will develop regression models using longitudinal data methods that adjust for correlation in BSID-III scores over time and for potential confounding by demographic characteristics. To explore the impact of digital literacy on healthcare utilization, the EHR will be reviewed to identify a subjects' number of well visits and their vaccination history.

To determine whether parent adversity, health literacy, and/or parent mental health modify the effects of digital versus standard literacy on language development, we will develop similar regression models using longitudinal data methods, but we will also fit interaction terms between study group and ACE score ( $\geq 4$ ), SAHL (high or low) and EPDS score ( $> 10$ ). To determine if parent-child reading activity mediates the association of intervention group assignment and language development, we will use mediation analysis with separate models regressing group assignment on language development, parent-child reading activity on group assignment, and group assignment on language development adjusted for parent-child reading activity.

Assuming a mean cognitive subscale on the BSID-III of 96, a power of 0.70, an alpha of 0.05, and a clinically significant difference of 7.5 points on the BSID-III between groups, we estimate that we will need to recruit a total sample size of 100 eligible children (50 in each group) to participate in the main RCT study (Figure 1). To attain thematic saturation in the Video Sub-study, we will recruit up to 40 participants 9-12 months of age. These 40 participants may be recruited external to the main study if we are unable to recruit up to 40 from the 100 enrolled in the main study in a timely fashion. All analyses will be conducted using Stata Statistical Software, version 13 (College Station, TX).

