**Figure 1**

Power	n
0.60	80
0.65	90
0.70	100

Assuming a mean cognitive subscale of the BSID-III, an alpha of 0.05, and an SD of 15.

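### The main BSID-III model adjusts only for unnamed demographics and leaves out clinic site and the baseline ACE, SAHL and EPDS scores, which gives up some precision in a trial planned at 0.70 power

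*Combined protocol and SAP*

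**What the plan says.** - **Main model.** Section 6.3 plans regression models for BSID-III that "adjust for correlation in BSID-III scores over time and for potential confounding by demographic characteristics". It gives no list of characteristics, no functional form and no rule for choosing them. The Abstract (Study Interventions and Measures) lists several demographic items, among them child age and sex, maternal education and family income category.
- **Stratification.** The Abstract (Study Design) and sections 3.1.1 and 3.2 stratify randomisation by clinic site. Section 6.3 does not name site.
- **Other baseline scores.** The Abstract and sections 3.1.3.1 and 3.1.4 place ACE, SAHL and EPDS at baseline. Section 6.3 uses them only in effect-modification models, cut at ACE 4 or more, SAHL high or low, and EPDS above 10.
- **Outcome.** BSID-III is scheduled once, at the second study visit (sections 4.2 and 6.1), so there is no baseline Bayley score to adjust for.
- **Sample size.** Section 6.3 assumes "a power of 0.70, an alpha of 0.05, and a clinically significant difference of 7.5 points on the BSID-III between groups", and Figure 1 adds "an alpha of 0.05, and an SD of 15". No covariate contribution and no dropout allowance enter the calculation.
- **Reading activity.** Section 5.1.4 reports for StimQ a "moderate correlation with the Bayley Scales of Infant Development" (r=0.52). Section 3.1.4 says "Parents will complete measures of reading activity at baseline", without naming an instrument.

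**The concern.** In a randomised comparison the main reason to adjust is that a baseline variable predicts the outcome, and the choice should be made in advance. Section 6.3 instead presents adjustment as control of confounding by an open set of demographics.

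Three things follow. The stratification factor is missing, although a standard error should reflect how the trial was randomised. Three scores that the protocol itself considers relevant to language development are absent from the main effect model. And because the demographics are not named, the primary estimate depends on choices that could still be made after the outcomes are seen.

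At 0.70 power, a true 7.5-point difference would be missed about three times in ten even with complete follow-up. Figure 1 puts power at 0.65 for 90 children, the number left if follow-up is 90%.

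**Working it through.** **Inputs from the documents.** Difference 7.5, alpha 0.05, power 0.70 and 50 per arm (section 6.3); SD 15 (Figure 1). Sidedness is not stated; two-sided reproduces the plan's figures.

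**Reproducing the plan.** SE = 15 × sqrt(2/50) = 3.0, and 7.5/3.0 = 2.5. Two-sided power is 0.705 by the normal approximation and 0.697 by the noncentral t. The normal formula returns exactly 100 for power 0.70. Totals of 80 and 90 give 0.598 and 0.650 (noncentral t), matching Figure 1. A one-sided test would give 0.804 at N=100 and does not fit.

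**Effect of adding covariates.** The added correlation r of the three scores with BSID-III is an assumption, since the documents give none. Residual SD = 15 × sqrt(1 − r²). N for 0.70 uses the normal formula.

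| Assumed added r | Residual SD | Power at N=100 (noncentral t) | N for 0.70 |
|---|---|---|---|
| 0 | 15.00 | 0.697 | 100 |
| 0.1 | 14.92 | 0.701 | 98 |
| 0.2 | 14.70 | 0.714 | 96 |
| 0.3 | 14.31 | 0.737 | 90 |
| 0.4 | 13.75 | 0.771 | 84 |

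**Starting from a model with demographics.** The table starts from no adjustment, whereas the plan already adjusts for demographics. If demographics explained 10% of the variance (assumed), power would already be 0.750 (normal approximation), and an added partial r of 0.1 to 0.4 would take it to 0.754 to 0.820. At 20% the range is from 0.798 to between 0.802 and 0.862. Overlap between the scores and demographics would also lower the partial r itself.

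**Cost of the extra terms.** Site (three clinics, two coefficients) plus three scores adds k = 5 coefficients. Residual degrees of freedom fall from 98 to 93, which changes power by no more than about 0.001. Chance imbalance costs more: for covariates unrelated to arm, variance grows on average by 1 + k/(N − k − 3) = 1 + 5/92 = 1.054. With that charge, power over r = 0.1 to 0.4 is 0.678 to 0.748, and break-even is r = sqrt(1 − 1/1.054) ≈ 0.23. Stratification should make site nearly free. For the three scores alone the factor is 1 + 3/94 = 1.032 and break-even is about 0.18.

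**Is StimQ available at baseline?** Section 3.1.4 alone says that reading activity is measured then. The baseline lists in the Abstract and sections 3.1.1, 3.1.3.1 and 4.1 omit it. The Abstract and sections 4.2 and 6.2 place StimQ about one month after the 6, 9 and 12 month visits, which is after allocation and after the first book is due. Section 6.3 treats reading activity as a possible mediator. If a pre-allocation StimQ existed and r=0.52 applied in full, residual SD would be 12.81 and power 0.826 (noncentral t; 0.833 by the normal approximation).

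**The case against.** **The gain is unproven and may be small.** This stands. No correlation is given for ACE, SAHL or EPDS, demographics may already carry part of their information, and at a low r the extra terms roughly pay for themselves or cost a little. The case for site and for naming the covariates in advance does not depend on that size.

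**Leaving out a prognostic covariate does not bias a randomised comparison.** Also correct. The point is about precision and prespecification, not bias.

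**Stronger readings that the documents do not support:**
- A reader might infer that the plan ignores a ready baseline predictor with r=0.52 and so forgoes power of 0.83. StimQ is not clearly collected before allocation. The 0.52 is a psychometric figure with no stated child age or time gap. Adjusting for a StimQ taken after allocation could remove part of the effect being estimated.
- A reader might infer that covariates will be picked on observed imbalance. Section 6.3 does not say so; it only leaves room for it.
- Section 3.1.1 states "Randomization will ensure equivalence between groups on measured and unmeasured characteristics". That is too strong for 50 per arm: a characteristic present in half of families has an arm difference with SD sqrt(2 × 0.25/50) = 0.10. Rewording it would change no planned analysis.
- Language of assessment might look like a free covariate. Families may speak English or Spanish, but the documents do not list the language used for the BSID-III as a recorded baseline variable.

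**Conclusion.** The concern holds as a matter of precision and prespecification. The main BSID-III model omits the stratification factor and three baseline scores already in hand, and leaves its demographic covariates unnamed. On an assumed added correlation of 0.1 to 0.4, power at N=100 would be about 0.70 to 0.77 against 0.70 unadjusted. That range does not charge for chance imbalance, and less gain is expected over a model that already adjusts for demographics. It rests on SD 15, a 7.5-point difference, a two-sided 0.05 test and complete follow-up. If the added correlation were 0.3, N for 0.70 power would fall to 90, enough to offset a 10% loss. Power of about 0.83 is a best case, conditional on a StimQ measured before allocation, which the documents do not establish.

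**What to change.** 1. In section 6.3, fix the primary model's covariates before any BSID-III outcome is examined: arm, clinic site, named demographics (including maternal education), and baseline ACE, SAHL and EPDS as continuous scores. Section 3.2 describes no blinding, so the lock should be tied to outcome access rather than to unblinding.
2. State that covariates will not be added or dropped because of observed imbalance.
3. Specify the baseline EPDS, because section 4.2 repeats it at the second visit. State that the baseline questionnaires are completed before the envelope is opened; sections 3.1.3.1 and 4.1 mention assignment first.
4. Reconcile section 3.1.4 with the Abstract and sections 3.1.1, 3.1.3.1, 4.1, 4.2 and 6.2 on whether StimQ is taken at baseline. Include it only if it is measured before allocation.

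Items 1 and 2 need only wording and use a few degrees of freedom out of 98, with the small variance charge shown above. Item 3 may require a change in the order of the first visit. Item 4 is wording if a pre-allocation StimQ is already being taken; otherwise using it would need an extra administration.

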## **5 STUDY EVALUATIONS AND MEASUREMENTS**

### **5.1 Screening and Monitoring Evaluations and Measurements**

#### **5.1.1 Parental Adversity (ACE)**

The 9 ACE questions query adults as to their exposure to 9 different adverse childhood experiences (economic hardship, domestic violence, parent mental health, discrimination, parent substance abuse, divorce, parent death, parent incarceration, and neighborhood violence) and are contained in the 2011-12 National Survey of Children's Health, a nationally representative telephone survey.

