#### **5.1.3 Parental Depressive Symptoms (EPDS)**

The Edinburgh Postnatal Depression Scale (EPDS) is a validated 10-item scale for postpartum depression symptoms with scores  $\geq 9$  having a sensitivity of 97% and specificity of 43% for major or minor depression.

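### Section 6.3 tests effect modification with dichotomised ACE, SAHL and EPDS and gives no reason for the cuts; if modification is roughly linear in the score, this loses about a third to over a half of the information on each interaction

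*Combined protocol and SAP*

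**What the plan says.** Section 6.3 (Statistical Methods) sets out to determine whether parent adversity, health literacy or parent mental health modifies the effect of arm on language development. It will "fit interaction terms between study group and ACE score" at 4 or more, SAHL as high or low, and EPDS above 10. It gives no reason for any cut and does not say where high SAHL begins. It also does not say which EPDS measurement is meant.

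Finer data are collected for at least two of the three:

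- **ACE (5.1.1):** "The 9 ACE questions query adults as to their exposure to 9 different adverse childhood experiences", so a count from 0 to 9 is available.
- **EPDS (5.1.3):** it "is a validated 10-item scale for postpartum depression symptoms". The section then describes scores of 9 or more as "having a sensitivity of 97% and specificity of 43% for major or minor depression". It reports no accuracy for a cut above 10.
- **SAHL (5.1.2):** described as a validated measure in English and Spanish, with no scoring or cut given.

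Sections 4.2 and 7.2 show that EPDS is taken both at baseline and at the second (final) study visit.

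The sample size in 6.3 is for the main effect only: "a power of 0.70, an alpha of 0.05", and "a clinically significant difference of 7.5 points on the BSID-III between groups", giving 100 children. No power is stated for the interactions.

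**The concern.** A binary modifier treats everyone on the same side of the cut as alike. If the arm effect changes gradually with adversity, literacy or depressive symptoms, the differences within each side are thrown away, and the answer depends on where the cut falls. With about 100 children and a design at 70% power for the main effect, the interactions have little information to spare.

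Three gaps add to this:

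- An undefined SAHL cut leaves room to choose it after the data are seen.
- A parent scoring 9 or 10 on the EPDS lies above the cut-off described in 5.1.3 and below the one used in 6.3.
- The second EPDS is taken after randomisation and could be affected by arm, so only the baseline value is a clean modifier.

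What is at stake is how the effect-modification results are read, in particular whether a null interaction is taken as evidence that the arm effect is the same for all families.

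**Working it through.** **1. The plan's own figure.** Inputs from 6.3 and Figure 1: difference 7.5, SD 15, alpha 0.05, 50 per arm. Standard error = 15 × √(2/50) = 3.0; 7.5/3.0 = 2.5; two-sided normal power = Φ(2.5 − 1.96) = 0.705, or 0.697 by t-test. The stated 0.70 for 100 children reproduces. The plan does not state sidedness, but a one-sided test would give 0.804, so two-sided is the reading that fits.

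**2. Assumptions not in the documents.** The share p above each cut is unknown; I show 0.15, 0.30 and 0.50. The score is taken as normal, modification as linear in the score, and the modifier as balanced across arms. SD 15 is used as the residual SD.

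**3. Information kept by the split.** With φ the normal density and z the cut point, the share kept is φ(z)² / [p(1 − p)]:

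- p = 0.15: 0.2332² / 0.1275 = 0.426 (57% lost)
- p = 0.30: 0.3477² / 0.21 = 0.576 (42% lost)
- p = 0.50: 0.3989² / 0.25 = 0.637 (36% lost)

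**4. Power with the binary term.** SE = 15 × √[4/(100p) + 4/(100(1 − p))]. Power is the two-sided normal approximation.

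**5. Power with the score.** The slope per SD of the score has SE 2 × 15/√100 = 3.0. The mean score differs between strata by φ(z)/[p(1 − p)] SDs. The slope matching a given difference in arm effect between strata is that difference divided by this gap. For 7.5 points at p = 0.50: 7.5/1.596 = 4.70; 4.70/3.0 = 1.567; power 0.35.

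| p | SE, binary | Gap (SDs) | Power for 7.5 points: binary / score | Power for 15 points: binary / score |
|---|---|---|---|---|
| 0.15 | 8.40 | 1.829 | 0.15 / 0.28 | 0.43 / 0.78 |
| 0.30 | 6.55 | 1.656 | 0.21 / 0.33 | 0.63 / 0.86 |
| 0.50 | 6.00 | 1.596 | 0.24 / 0.35 | 0.71 / 0.88 |

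**6. Does normality drive the result?** Skewed counts were simulated from negative binomial distributions with assumed means, limited to each scale's range. The squared correlation between score and indicator gave a loss of about 35-41% for EPDS above 10 (means 5 to 8) and 33-54% for ACE 4 or more (means 1 to 2.5). The loss is of the same order without normality. For SAHL it cannot be computed, because neither scoring nor cut is given.

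**7. Does the EPDS mismatch drive the loss?** In the same simulations the EPDS information kept was 0.64-0.65 with a cut at 9 or more and 0.59-0.65 with a cut above 10. Moving the cut recovers little; the loss comes from cutting at all.

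**The case against.** The strongest case against is that the gain depends on a linear gradient. The information kept is a squared correlation between score and indicator, so it works both ways: if modification is truly a step at the chosen cut, the binary term is the efficient one and a linear score would keep only the same 43-64%. At 100 children a quadratic term has little power to tell the two apart. This stands as a real downside. It does not rescue the plan, which offers no evidence for a step at any of the three cuts.

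Second, the size of the loss rests on assumed shares and a distribution that the documents do not give. That also stands, and is why a range is shown.

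Third, the 15-point row is twice the plan's own clinically significant difference. At 7.5 points both methods are weak. A reader might infer that continuous scores would make these tests adequate, or that the cuts alone make a null result uninformative. Neither follows: the dominant limit is the sample size, and a null result at 7.5 points would say little under either method.

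Fourth, effect modification is not among the four specific aims or the listed endpoints, and binary strata fixed in advance are easy to report and limit searching for cut-points. The consequence is indeed confined, but 6.3 does state a purpose of determining effect modification, and the SAHL cut is not in fact fixed.

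Finally, the abstract lists EPDS with ACE and SAHL as baseline measures, so baseline is the natural reading. One explicit phrase would settle it.

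**Conclusion.** The point holds. Section 6.3 reduces all three modifiers to binary terms without justification. Under linear modification and a normal score, this discards 36% to 57% of the information on the interaction as the share above the cut goes from 50% to 15%. Fitting the scores is the better default, but it improves power for a 7.5-point interaction only to about 0.28-0.35, so the tests remain exploratory.

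The EPDS discrepancy is a separate matter of consistency. A reader might infer that 5.1.3 names 9 or more as the validated cut-off, and that departing from it causes the lost information. The documents support neither. Section 5.1.3 calls the scale validated and reports accuracy at 9 or more; it does not adopt that value as the study's rule. Nor does its reported specificity of 43% make it an obvious choice for an analysis stratum. What can be said is that 9 or more is the only cut-off whose accuracy the protocol reports, that 6.3 uses another, and that no reason is given.

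Only the effect-modification analyses are affected. The primary comparison and the sample size of 100 are not.

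**What to change.** In section 6.3:

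- Make arm-by-score interactions the main effect-modification analysis, with the ACE count, SAHL score and **baseline** EPDS total as continuous terms.
- Report each interaction slope with a 95% confidence interval, and show model-based arm effects at a few illustrative score values named in advance.
- Check linearity with a plot or a quadratic term, acknowledging that the check is weak at this sample size.
- Label these tests exploratory, and say that a null interaction is not evidence of a uniform effect.
- If binary displays are kept as a supplement, define the SAHL cut before the data are seen and give a reason for each cut. For EPDS, reconcile 5.1.3 and 6.3 or justify the difference.

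The cost is SAP wording only, with no new data collection, visits or sample size. The price in analysis is the linearity assumption and some efficiency if the true pattern is a step at the cut.

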## 4.2 Study Treatment Phase

- Implement an EHR alert to remind clinicians which arm (digital or standard) the patients are in at time of well visits at 6, 9 and 12 months.
- Provide developmentally appropriate standard books or e-books and a bookmark to clinicians to give to participants at 6, 9, and 12 month well visits.
- Parents will complete measures of reading activity (StimQ and ERPQ) via REDCap survey sent to their email about 1 month subsequent to the time the child has, or is age-eligible for, their 6 and 9 month well visits.
- Phone calls and/or text messages will be made to all participants throughout the study to remind them to schedule and/or attend well visit, and for other study-related reminders.
- Selected parents will complete a videotaped reading task at a scheduled time convenient to the participant and after the participant becomes age-eligible for their 9 month well visit. For parents enrolled external to the larger randomized control trial, this will be the only study visit completed by these participants. These participants will complete the study related questionnaires, including the demographic questionnaire, the ACE, SAHL, EPDS, StimQ and ERPQ, at the time of this study visit. Participants enrolled in the sub-study (either within the RCT or externally) will additionally complete the paper-based DialogPR-I at the time of their video sub-study visit.
- Contact participant after the child has, or is age-eligible for, the 12 month well visit to schedule the second study visit.
- At the second study visit, about 1 month after the child has, or is age-eligible for, the 12 month well visit, parents will complete measures of reading activity (StimQ, ERPQ and DialogPR-I) in addition to a measure concerning depressive symptoms (EPDS), and their child will receive a developmental assessment (BSID-III) administered by the study's Early Childhood Assessor.

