### **6 STATISTICAL CONSIDERATIONS**

#### **6.1 Primary Endpoint**

The primary endpoint for the randomized control trial will be the BSID-III scores at the second study visit when the child is between 12 and 18 months, 30 days of age.

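### Two of the three mediation models in Section 6.3 are written with the randomised arm as dependent variable, and the indirect effect and the mediator's time point are not specified

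*Combined protocol and SAP*

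**What the plan says.** Section 6.3 gives the purpose: "To determine if parent-child reading activity mediates the association of intervention group assignment and language development, we will use mediation analysis". It then lists three models. The first two are "separate models regressing group assignment on language development, parent-child reading activity on group assignment"; the third is "group assignment on language development adjusted for parent-child reading activity". Nothing else in the plan specifies the mediation analysis. It does not say which reading instrument or time point is the mediator, how an indirect effect will be calculated, what interval or test will accompany it, or which covariates enter these models.

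On timing, Section 6.1 defines the outcome as "BSID-III scores at the second study visit when the child is between 12 and 18 months, 30 days of age". Section 4.2 collects reading activity at that same visit ("parents will complete measures of reading activity (StimQ, ERPQ and DialogPR-I"). It also schedules StimQ and ERPQ surveys earlier, "about 1 month subsequent to the time the child has, or is age-eligible for, their 6 and 9 month well visits". Section 3.1.4 adds a baseline measurement ("Parents will complete measures of reading activity at baseline, and via the REDCap survey sent by email"), which the baseline lists in Sections 3.1.3.1 and 4.1 do not mention.

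**The concern.** A mediation analysis of arm, then reading, then language needs two paths: arm to reading, and reading to language given arm. The second comes from a model with language as the outcome and both arm and reading as predictors. As worded, the plan has no such model. An analyst who codes the section literally gets coefficients on the scale of arm probability per BSID-III point, which cannot be combined with model 2 into an indirect effect.

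Two gaps add to this. Without a stated indirect-effect estimator and interval, the criterion for mediation can be chosen after the data are seen. Without a named time point, the mediator may be the StimQ taken at the BSID-III visit, which does not clearly precede the outcome. What is at stake is the explanation of an arm difference, not the estimate of that difference.

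**Working it through.** **1. The plan's own figure.** The only sample-size figure is for the primary comparison. With a difference of 7.5 (Section 6.3), SD 15 (Figure 1) and two-sided alpha 0.05 (sidedness is not stated, but two-sided is what reproduces the figures), n per group = 2 x (1.960 + 0.524)^2 x (15/7.5)^2 = 49.4. This rounds up to 50, or 100 in total at power 0.70. The same formula gives 80 and 90 at 0.60 and 0.65, matching Figure 1. The mediation analysis has no figure of its own.

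**2. The three models side by side.**

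| Model | As worded (outcome ~ predictors) | Needed |
|---|---|---|
| 1 | arm ~ BSID-III | BSID-III ~ arm (total effect c) |
| 2 | reading ~ arm | reading ~ arm (path a) |
| 3 | arm ~ BSID-III + reading | BSID-III ~ arm + reading (direct effect c', path b) |

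If the wording is read in the opposite sense, models 1 and 3 come right and model 2 becomes wrong. No single convention makes all three correct.

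**3. What the literal models return.** This is an illustration, not a prediction. From the plan: a 7.5-point difference, SD 15, and the StimQ-Bayley correlation of 0.52 (Section 5.1.4), used only to set a scale. Assumed: the digital arm is lower, and a = -0.5 SD of reading.

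- b = 0.52 x 15 = 7.8 points per SD
- indirect effect a x b = -0.5 x 7.8 = -3.9 points
- c = -7.5, so c' = -7.5 + 3.9 = -3.6

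In 400,000 simulated dyads the correctly ordered models gave c = -7.52, c' = -3.61 and a x b = c - c' = -3.91.

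Literal model 1 has slope (-7.5 x 0.25)/(225 + 7.5^2 x 0.25) = -1.875/239.06 = -0.0078 (simulated: -0.0079). Literal model 3 gave -0.0051 for BSID-III and -0.0763 for reading. The two ways of forming an indirect effect then give:

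- difference: -0.0079 + 0.0051 = -0.0028
- product: -0.501 x -0.0763 = +0.038

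Neither is the indirect effect, and the product has the wrong sign.

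**4. What the literal models keep.** In ordinary least squares without further covariates, swapping arm and language leaves the t-statistic for their association unchanged (-158.7 both ways unadjusted, -86.6 both ways adjusted for reading). The total and direct associations can therefore still be tested. The reading-to-language path is lost: its t was 384.7 in the correct model 3, whereas the reading coefficient in the literal model 3 had t = -86.4 and measures something else.

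**5. Timing.** The surveys after the 6- and 9-month visits precede the BSID-III; the 12-month measurement does not. Section 6.3 chooses none of them.

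**6. Limits that remain after correction.** Randomisation protects path a but not path b. In 3,000 simulated trials of 100 dyads with a = 0.5 SD, no effect of reading or arm on language, and an unmeasured cause shared by reading and language (assumed loadings 0.6), both paths were significant in about 68%. With no such confounding and no direct effect, joint significance of the two paths ranged from 26% (a = 0.3 SD, standardised b = 0.30) to 98% (a = 0.8 SD, b = 0.52).

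**The case against.** The strongest reply is that this is a slip of wording. The purpose clause gives the direction plainly, model 2 is correct, and the preceding sentence on effect modification treats language as the outcome and study group as the predictor. Few analysts would model a randomised arm as the result of a later test score. In the evident direction the three models yield a, b, c and c', and the point estimate a x b or c - c' follows. Earlier StimQ surveys are already scheduled. Mediation is not among the aims in Section 2 or the endpoints in Sections 6.1 and 6.2.

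Most of this stands, and it rules out three stronger readings that a reader might infer:

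- *That the planned analysis cannot show mediation.* This holds for the literal wording only.
- *That the same-visit mediator is a flaw of the design.* It is an open choice, because Section 4.2 already provides earlier measurements.
- *That three separate models imply a stepwise procedure requiring a significant total effect, with a loss of power.* Section 6.3 states no such requirement, and the size of any loss would depend on the total effect one assumes.

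The reply does not remove the defect. This sentence is the plan's only mediation specification, it contradicts itself on direction, and the estimator, interval and mediator time point remain unstated even when it is read charitably.

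**Conclusion.** The point holds in a limited form. Models 1 and 3 are reversed; run as written, they omit the reading-to-language path and give no indirect effect. Once reordered, the models supply a point estimate, but the plan still does not commit to reporting one, to an interval, or to a mediator measured before the outcome.

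The numbers (-3.9 points against -0.0028 or +0.038) rest on assumed paths and show the kind of error, not its size in this trial. The reversal and the omissions rest on the text alone. The analysis is supporting, so the text should be corrected before analysis, but the primary comparison, the sample size of 100 and data collection do not change. Confounding between reading and language remains possible after any rewording and limits how firmly a mediation result can be stated.

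**What to change.** Restate the mediation models in Section 6.3 as:

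- (a) BSID-III on arm
- (b) StimQ on arm
- (c) BSID-III on arm and StimQ

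Adjust all three for clinic site and the baseline covariates already collected (demographics, ACE, SAHL, EPDS). If the baseline reading measure in Section 3.1.4 is in fact taken, include it too.

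Report the indirect effect as the product of the arm-to-StimQ and StimQ-to-BSID-III coefficients, with a bootstrap 95% confidence interval, and do not require a significant total effect. Use the StimQ from the survey after the 9-month visit as the main mediator and the 12-month StimQ as a sensitivity analysis. State that mediator-outcome confounding cannot be excluded.

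The cost is a paragraph of text and a few lines of code, with no new data. The one real downside is that the 9-month StimQ misses reading after the third book, given for the 12-month visit; the sensitivity analysis covers that period at the price of weaker time order.
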